## 8. PHARMACOKINETIC ANALYSES

The reconciliation of the PK Case Report Form (CRF) and SMS2000 data will be performed by, or under the direct auspices of, Clinical Pharmacology Sciences and Study Operations (CPSSO), GlaxoSmithKline.

The merge of PK concentration data and CRF data will be performed by, or under the direct auspices of, Clinical Statistics (Programmer), GlaxoSmithKline.

Derivation of pharmacokinetic parameters will be performed by, or under the direct auspices of, Clinical Pharmacology Modelling and Simulation (CPMS), GlaxoSmithKline.

Statistical analysis of pharmacokinetic parameters will be performed by, or under the direct auspices of, Clinical Statistics (Statistician), GlaxoSmithKline.

Concentration and PK parameter data will be reported for specified Pharmacokinetic populations in the OLI and Injection phases.

### 8.1. Drug Concentration Measures

Plasma CAB and RPV concentration values will be summarized with descriptive statistics by study phase, treatment, visit, and planned timepoint for the PK Concentration Population (PC). These concentration values will be determined directly from concentration-time data from each analyte. Descriptive statistics including the n, mean with associated 95% CI, standard deviation, median, minimum, maximum, geometric mean with associated 95% CI, standard deviation of logarithmically transformed data, 5th/95th percentiles and the geometric coefficient of variation (CVb(%))).

Individual concentration-time profiles and median/mean profiles from each analyte in each study phase will be plotted for the PK Concentration (PC) Population. Each of the figures will contain one plot on the untransformed scale (i.e. a linear plot) and one plot on the log transformed scale (i.e. semi-log plot). Actual assessment times will be used in the individual concentration-time plots. Nominal times will be used for the purposes of summarization and in mean and median plots. See [Appendix 4: Data Display Standards & Handling Conventions](#). for details on pharmacokinetic figure and table displays.

## 8.2. Deriving and Summarizing Pharmacokinetic Parameters

Pharmacokinetic parameters will be derived by standard non-compartmental analysis according to current working practices and using the currently supported version of WinNonlin 6.3 or higher (Pharsight, Inc., Cary, NC). All calculations of non-compartmental PK parameters will be based on actual sampling times. Pharmacokinetic parameters listed will be determined from the plasma concentration-time data, as data permits. The following PK parameters will be derived and displayed for the PP Population as data permits:

**Table 7      Derived PK Parameters**

Parameter	Parameter Description	OLI Phase	Injection Phase
$C_{\max}$	Maximum observed concentration	Day 1	Overall
$t_{\max}$	Time of occurrence of $C_{\max}$	Day 1	Overall
$AUC_{0-\infty}$	Area under the concentration time curve from time zero to infinity	Day 1-2	Overall
$AUC_{0-t}$	Area under the concentration time curve from time zero to last quantifiable time point	Day 1-2	Overall
$t_{1/2}$	Terminal phase half-life	Day 1-2	Overall
$K_A$ LA	Absorption rate constant, Long-acting	NA	Overall
$\lambda_z$	Terminal phase rate constant	Day 1-2	NA
C24	Concentration at OLI Phase 24-hour timepoint	Day 2	NA
$C_{\tau}$	Trough concentrations ( $C_{\tau}$ ) at OLI Phase Day 29	Day 29	NA

NOTES: NA: Not Applicable

- Additional parameters may be included as required.

Primary Pharmacokinetic endpoints include the following PK parameters from Injection Phase:

- Maximum observed concentration ( $C_{\max}$ ) and time of maximum observed concentration ( $t_{\max}$ ) in plasma
- Area under the concentration – time curve from time zero to last quantifiable time point ( $AUC_{0-t}$ ) through the follow-up phase
- Area under the concentration – time curve from time zero to infinity ( $AUC_{0-\infty}$ )
- Apparent terminal phase half-life ( $t_{1/2}$ ) and absorption rate constant ( $K_A$  LA))

PK parameters such as  $C_{\max}$  and AUC should be reported in  $\mu\text{g}/\text{mL}$  and  $\mu\text{g}^*\text{h}/\text{mL}$  for CAB and in  $\text{ng}/\text{mL}$  and  $\text{ng}^*\text{h}/\text{mL}$  for RPV. Other PK parameters such as  $t_{\max}$  and  $t_{1/2}$  should be reported in hours and  $K_A$  LA and  $\lambda_z$  parameters in  $/\text{h}$  for both CAB and RPV.

### **8.3. Statistical Analyses**

All the derived pharmacokinetic parameters will be summarized and listed for the PP population by study phase and treatment. For each of these PK parameters, with the exception of  $t_{max}$ , the following descriptive summary statistics will be calculated for each treatment: n, arithmetic mean with associated 95% CI, standard deviation, median, minimum, maximum, geometric mean with associated 95% CI, standard deviation of logarithmically transformed data, and the geometric coefficient of variation ( $CV_b(\%)$ ). For  $t_{max}$ , the n, median, minimum, and maximum summary statistics will be provided.

Data display specifications for derived PK parameter summaries and listings are given in [Appendix 9](#) of this RAP

PK samples collected outside the protocol defined time-windows and/or other protocol deviations will be reviewed by the study team to determine whether the sample will be excluded from PK analyses. PK reporting will also consider planned Quality Tolerance Limit (QTL) outcomes affecting study data quality. Details are found in the QTL Report.

### **8.4. Strategy for Intercurrent Events – Covid-19 Complications**

[figure not shown]
While incidents of Covid-19 could be expected to affect subject safety, its effect on CAB + RPV PK concentrations is unknown. Given the small study sample size implying less likelihood that a subject acquires Covid-19 through the course of the study, the benefit of a sensitivity analysis for subjects that acquire Covid-19 during the course of their PK sampling appears minimal. Should more information become available and/or the clinical need arise, this RAP may be amended to include Covid-19 PK sensitivity analyses in order to further understand any potential interacting effects.

## 9. HEALTH OUTCOMES ANALYSES

Health outcomes questionnaire data will be summarised and listed by, or under the direct auspices of, Clinical Statistics, GlaxoSmithKline. The health outcomes analyses will be based on the Safety population, unless otherwise specified. All questionnaire data will be listed by subject, item, treatment, and timepoint as applicable.

No formal statistical analysis of the health outcomes data will be conducted. The precise format and content of health outcomes tables and listings are shown in [Appendix 5](#) of the RAP.

CCI

## 11. APPENDICES

### 11.1. Appendix 1: Schedule of Activities

#### 11.1.1. Screening and Oral Lead-in Phase

Study Period	Screening 		Oral Lead-in 			Day 29	Early Withdrawal 	Washout Period
			Dosing Days 1-28					
Visit Window	Within 30 days of oral lead-in	Day -1	Day 1	Day 2	Day 14	Within 24 hours of the Day 28 last dose	EW	10 – 14 days
Informed Consent	X							
Demographics	X							
Medical / Medication / Drug / Alcohol History	X							
Inclusion/Exclusion Criteria 	X		X					
Height, Weight, BMI	X							
Physical Exam	X		X					
Vital Signs 	X		X	X	X	X	X	
12-Lead ECG	X		X			X		
Drug / Alcohol Screen 	X		X					
Pregnancy Test 	X		X		X	X		
Testing for SARS-CoV-2 	X	X						
Hepatitis B, Hepatitis C Screening	X							
HIV Test	X							
Urine Dipstick	X							
Hematology with differential; Clinical Chemistry Tests 	X		X	X	X	X	X	
Coagulation Tests	X							
Admit to clinic		X						
Dispense Oral lead-in IP			X					

Study Period	Screening 		Oral Lead-in 			Day 29	Early Withdrawal 	Washout Period
			Dosing Days 1-28					
Visit Window	Within 30 days of oral lead-in	Day -1	Day 1	Day 2	Day 14	Within 24 hours of the Day 28 last dose	EW	10 – 14 days
Administer oral CAB + RPV 			X	X	X			
Dispense Medication Dosing Diary				X				
Drug accountability/ pill count/review drug diary				X	X	X		
Blood plasma PK sampling 			X	X	X	X	X	
AE Assessment 			X	X	X	X	X	
Concomitant Medication Review			X	X	X	X	X	
Genetic sample 			X					
Discharge from the clinic				X				

1. Screening may occur over more than one visit but within 30 days of the first dose of oral CAB and RPV in the oral lead in phase.
2. Eligibility criteria must be carefully assessed at the Screening visit and confirmed at the Day 1 Oral lead-in phase visit and re-confirmed prior to injection.
3. Prior to administering the first oral dose of CAB and RPV, study personnel must verify the following pre-dose assessments to be within normal limits prior to administration: vital signs, pregnancy test (negative; Females of Reproductive Potential (FRP) only. The results of the Drug/Alcohol screen, hematology with differential, and clinical chemistry tests on Day 1 are not required prior to administering the first oral doses of CAB and RPV but should be drawn prior to CAB and RPV administration.
4. Following the second test for SARS-CoV-2, participants will be advised to self-quarantine until entrance to the unit while awaiting final testing clearance.
5. Oral CAB and RPV dosing Days 1 to 28. Day 1, Day 2, and Day 14 doses should be administered in the clinic.
6. PK sampling – On Day 1 - 1h, 2h, 3h, 4h, 6h, 8h, and 12h, and Day 2 PK between 22-26 h from first oral dose. On Day 14 pre-dose samples. Day 29 assessments should occur between 22-26 hours from the last dose on Day 28. Total of 20 PK samples (10 for CAB, 10 for RPV assay) will be collected during oral lead-in phase. Please refer to Protocol Section 8.4 for permitted PK window for OLI phase.
7. AE assessment will include a brief, symptom-directed physical exam as needed.
8. Genetic sample - collect the sample at the earliest convenient time after the first dose in the oral lead in phase on Day 1.
9. If a participant is withdrawn prior to receiving the CAB LA and/or RPV LA injection, a follow-up/withdrawal visit should be scheduled 10-14 days after the last oral dose of CAB and RPV.

## 11.1.2. CAB LA + RPV LA Injection Phase and Follow- up

Procedures	Injection Phase						Follow-up							
	Week 52	Week 36	Week 24	Week 12	Week 8	Day 28 (Week 4)	Day 22	Day 17	Day 15	Day 10	Day 7/8	Day 5	Day 4	Day 2
Permitted window for PK collection					± 3 days			± 2 h	± 2 h	± 2 h	± 2 h			
Interim Medical/Medication/ Drug / Alcohol History 														
Pregnancy Test	X													
12-Lead ECG 	X													
HIV Test	X													
Testing for SARS-CoV-2														
Hematology; Clinical Chemistry	X					X			X		X		X	
Vital Signs 	X			X	X	X	X		X		X	X	X	
Administer CAB LA + RPV LA 	X													
CCI				X 	X 	X 	X 							
Injection site reaction assessment		X	X	X	X	X	X	X	X	X	X	X	X	X
AE Assessment 		X	X	X	X	X	X	X	X	X	X	X	X	X
Concomitant Medication Review	X	X	X	X	X	X	X	X	X	X	X	X	X	X
Blood plasma PK Sampling 	X	X	X	X	X	X	X	X	X	X	X	X	X	X

1. Participants who terminate before week 52 will be asked to return to the site for a withdrawal visit.
2. On Day 1, study personnel must verify the following pre-dose assessments to be within normal limits prior to injection: ECG, vital signs, pregnancy test (negative; FRP only), review AE assessment, and concomitant medications. If a clinical abnormality, clinically significant AE, or prohibited medication that precludes injection is observed/recoded, the medical monitor must be contacted for further instruction.
3. Participants will be asked to describe the comfort level with the injections received. **CCI**  
**CCI**
4. AE assessment will include a brief, symptom-directed physical exam as needed.
5. Total of 34 PK samples (17 each for CAB and RPV) will be collected through CAB LA + RPV LA Injection Phase and Follow-up.

## 11.2. Appendix 2: Assessment Windows

All assessments/events (including those from planned, unscheduled and withdrawal visits) will be assigned to assessment windows/analysis visits according to actual dates of collection rather than the nominal visit labels recorded on the eCRF or in the laboratory database. All assessment data, including unscheduled data will be presented in listings.

For parameters which are not scheduled to be assessed at a particular visit, the all-inclusive assessment windows will still be used; however, data displays summarizing measurements by visit will only report visits in which the parameter is a planned collection according to [Appendix 1: Schedule of Activities](#)

Note: Prior to visit slotting, assessments are first assigned to a study phase according to [Table 3](#).

### 11.2.1. Definitions of Assessment Windows

**Table 8 Assessment Windows for Screening and OLI Phase Data**

Parameter	Analysis Window	Target Period Day	Analysis Timepoint
Assessments assigned to Phase=Screening or OLI (per Table 3)			
All	OLI Phase Day <1	The day of earliest record	Screening
PK, Vital Signs, Labs, ECG	OLI Phase Day = 1	1	Day 1
PK, Vital Signs, Labs	OLI Period Day = 2	2	Day 2
PK	13 ≤ OLI Phase Day ≤ 15	14	Day 14
Vital Signs, Labs	3 ≤ OLI Phase Day ≤ 21	14	Day 14
PK	28 ≤ OLI Phase Day ≤ 30	29	Day 29
Vital Signs, Labs, ECG	22 ≤ OLI Phase Day	29	Day 29
If none of the above			Day X, where X=OLI Phase day

**Table 9 Assessment Windows for Injection & Follow-up Phase Data**

Parameter a	Analysis Window	Target Period Day	Analysis Timepoint
Assessments assigned to Phase=Injection (per Table 3)			
PK, Vital Signs, Labs, ECG, CCI	Injection Phase Day = 1	1	Day 1
PK, Vital Signs, CCI	Injection Phase Day = 2	2	Day 2
PK	Injection Phase Day = 4	4	Day 4
CCI	3 ≤ Injection Phase Day ≤ 4	4	Day 4
PK	Injection Phase Day = 5	5	Day 5
Vital Signs	3 ≤ Injection Phase Day ≤ 6	5	Day 5
CCI	5 ≤ Injection Phase Day ≤ 6	5	Day 5
ECG	2 ≤ Injection Phase Day	5	Day 5

Parameter a	Analysis Window	Target Period Day	Analysis Timepoint
PK	Injection Phase Day = 7	7	Day 7
PK	Injection Phase Day = 8	8	Day 8
CCI	7 ≤ Injection Phase Day	8	Day 8
Vital Signs	7 ≤ Injection Phase Day ≤ 9	8	Day 8
Labs	2 ≤ Injection Phase Day ≤ 10	8	Day 8
PK	Injection Phase Day = 10	10	Day 10
Vitals	10 ≤ Injection Phase Day ≤ 12	10	Day 10
PK	Injection Phase Day = 15	14	Day 15
Vital Signs	12 ≤ Injection Phase Day ≤ 16	14	Day 15
PK	Injection Phase Day = 17	17	Day 17
Vital Signs	17 ≤ Injection Phase Day ≤ 19	17	Day 17
Labs	11 ≤ Injection Phase Day ≤ 23	17	Day 17
PK	Injection Phase Day = 22	22	Day 22
Vital Signs	20 ≤ Injection Phase Day ≤ 25	22	Day 22
PK	Injection Phase Day = 28	28	Week 4
Vital Signs	26 ≤ Injection Phase Day	28	Week 4
Labs	24 ≤ Injection Phase Day	28	Week 4
	If none of the above		Day X, where X=Injection Phase Day
Assessments assigned to Phase=Follow-up (per Table 3)			
Vital Signs, Labs	(Date of Nominal Follow-up Week 4 Visit – CAB + RPV Injection Date) +2 ≤ Injection Phase Day ≤ 70	56	Week 8
PK	53 ≤ Follow-up Period Day ≤ 59	56	Week 8
Vital Signs, Labs	71 ≤ Follow-up Period Day ≤ 126	84	Week 12
PK	81 ≤ Follow-up Period Day ≤ 87	84	Week 12
Vital Signs, Labs	127 ≤ Follow-up Period Day ≤ 210	168	Week 24
PK	165 ≤ Follow-up Period Day ≤ 171	168	Week 24
Vital Signs, Labs	211 ≤ Follow-up Period Day ≤ 308	252	Week 36
PK	249 ≤ Follow-up Period Day ≤ 255	252	Week 36
Vital Signs, Labs, ECG	309 ≤ Follow-up Period Day	364	Week 52
PK	361 ≤ Follow-up Period Day ≤ 367	364	Week 52
	If none of the above		Day X, where X=Follow-up Phase Day
NOTES:			

 
OLI Day, Injection Day, and Follow-up Day are defined in Section 11.5.1.
 
			

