## 11.3. Appendix 3: Study Phases and Treatment Emergent Adverse Events

### 11.3.1. Study Phases

All assessments and events (including those collected as planned, early withdrawal and unscheduled visits) will be classified in study phases according to [Table 3](#).

Assessments/events are assigned to study phases sequentially, starting from the top of each table.

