## 11.5. Appendix 5: Derived and Transformed Data

### 11.5.1. General

Multiple Measurements at One Analysis Time Point

 
If there are multiple measurements within a time window (per Section 11.2.1), the value closest to the target day for that window will be used. If values are the same distance from the target, then the mean of the measurements (for quantitative parameters including ECG values) or the worst-case of the measurements (for qualitative parameters) will be calculated and used in any derivation of summary statistics.
 
Only planned assessment timepoints (according to Appendix 2: Schedule of Activities) will be included in data displays summarizing measurements by visit.
 
Assessments not chosen for use in summary statistics will still appear in the associated listings.
 
All applicable valid assessments, irrespective of proximity to the target study day, will be used when categorizing values across visits, such as 'maximum grade during the intervention phase' or 'at any time post-baseline', and for any algorithm that has specific rules for which observation to use (e.g. LOCF).
 

Change from Baseline

 
Post-Dose Visit Value – Baseline
 
Unless otherwise specified, the baseline definitions specified in Section 6.2 will be used for derivations for endpoints / parameters.
 

Study Day

 
The Study Day of an event (e.g., lab assessment, vital sign, ECG, start date of AE) will be derived as the number of days between the date of the event and the Intervention Phase treatment start date as follows: 
 
If date of event <math>\geq</math> start date of study treatment, then 
 
Study Day = Date of Event - Intervention Phase Treatment Start Date +1
 
 
 
If date of event <math><</math> start date of study treatment, then 
 
Study Day = Date of Event - Intervention Phase Treatment Start Date
 
 
 
Note that the start date of each phase is on Study Day 1 and the day before this is Study Day -1; i.e., there is no Study Day 0.
 
 
 

Phase Day

 
Calculated as the number of days from First Dose Date of CAB + RPV for the respective phase (based on study period classifications in Table 3):
 

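### SAP Table 9 puts Injection Phase Day 12 in two vital-sign windows and prints Day 14 as the target for the Day 15 visit

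*SAP*

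**What the plan says.** SAP Appendix 2 (11.2) states that readings, including those from unscheduled and withdrawal visits, are "assigned to assessment windows/analysis visits according to actual dates of collection rather than the nominal visit labels".

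Table 9 sets the injection-phase windows. For vital signs the relevant rows are:

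- Day 10: "10 ≤ Injection Phase Day ≤ 12", target 10
- Day 15: "12 ≤ Injection Phase Day ≤ 16", target 14
- Day 17: "17 ≤ Injection Phase Day ≤ 19", target 17

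The Day 15 PK row has the window "Injection Phase Day = 15" and also prints target 14, a day outside its own window. At every other injection-phase visit in the table, the target equals the labelled visit day (28 for Week 4).

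When several readings fall in one window, SAP 11.5.1 says "the value closest to the target day for that window will be used". For ties it continues: "If values are the same distance from the target, then the mean of the measurements" (for quantitative parameters).

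Protocol 10.4.1 says that tabulated safety summaries contain scheduled assessments only. SAP 11.4.2, however, assigns unscheduled visits to study visits through these windows, and SAP 2.1 and its Table 1 list no change on this point.

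**The concern.** A visit-window table should send each reading to exactly one visit, and its target should be the visit day. The Day 15 vital-sign row fails on both counts, and the two faults act by different routes.

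The overlap lets one Day 12 reading count at two visits. The target of 14 lets a reading taken off schedule replace or dilute the reading taken on the planned day. What is at stake is whether the Day 10 and Day 15 lines of the vital-sign summaries (Table 3.37 for change from baseline) are uniquely defined and reproducible. It also matters whether they follow the protocol's limit to scheduled assessments.

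**Working it through.** **1. Coverage.** The inputs are the Table 9 vital-sign windows: Day 1; Day 2; Days 3–6; 7–9; 10–12; 12–16; 17–19; 20–25; and 26 onward. Checking each day from 1 to 30 against them, Day 12 is the only day that falls in two windows, and no day falls in none.

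**2. Is there a rule that settles Day 12?** SAP 11.5.1 chooses among readings inside one window and does not choose between windows. Stretching it across windows would not help, because |12 − 10| = |12 − 14| = 2. The SAP's only first-match rule, "Assessments/events are assigned to study phases sequentially, starting from the top of each table", is stated for study phases and not for visit windows.

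**3. Distances inside the Day 15 window.**

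| Reading day | Distance, target 14 (printed) | Distance, target 15 |
|---|---|---|
| 12 | 2 | outside the corrected window |
| 13 | 1 | 2 |
| 14 | 0 | 1 |
| 15 | 1 | 0 |
| 16 | 2 | 1 |

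With the printed target, Day 14 beats Day 15 and Day 13 ties with it. Days 12 and 16 lose to Day 15.

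**4. Reading patterns.** The corrected columns use windows 10–12 and 13–16 and target 15 for the Day 15 visit.

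| Reading days | Day 10 uses, as written | Day 15 uses, as written | Day 10 uses, corrected | Day 15 uses, corrected |
|---|---|---|---|---|
| 10, 15 (as planned) | 10 | 15 | 10 | 15 |
| 12 | 12 | 12 | 12 | none |
| 12, 16 | 12 | mean of 12 and 16 | 12 | 16 |
| 10, 12 | 10 | 12 | 10 | none |
| 10, 12, 15 | 10 | 15 | 10 | 15 |
| 10, 13, 15 | 10 | mean of 13 and 15 | 10 | 15 |
| 10, 14, 15 | 10 | 14 | 10 | 15 |

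Use at both visits needs a Day 12 reading, none on Days 10–11 and none on Days 13–15. A Day 16 reading only ties with it.

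Both edits are needed. With the overlap removed but target 14 kept, {14, 15} still selects Day 14 and {13, 15} is still averaged.

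**5. Which bound fits the table?** Midpoints of adjacent visit days:

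- (5 + 8)/2 = 6.5; the table cuts at 6/7
- (8 + 10)/2 = 9; Day 9 goes to the earlier visit
- (15 + 17)/2 = 16; Day 16 goes to the earlier visit
- (17 + 22)/2 = 19.5; the table cuts at 19/20
- (22 + 28)/2 = 25; Day 25 goes to the earlier visit

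For Days 10 and 15 the midpoint is 12.5, so Day 12 belongs with Day 10 and the Day 15 window starts at 13. The printed upper bound of 16 also fits a visit on Day 15. For a visit on Day 14, (14 + 17)/2 = 15.5 would end the window at 15.

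**6. Size.** About 15 participants are to be injected, so one reading is 1/15 = 6.7% of a visit's data. If one participant's Day 15 value is replaced by one differing by d, the visit mean moves by d/15. If the two are averaged, it moves by (d/2)/15 = d/30.

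**The case against.** The strongest reply is that Protocol 10.4.1 already keeps unscheduled readings out of safety tables, so an unscheduled Day 13 or Day 14 reading could not displace a scheduled one. Read alone, it does. But SAP 11.2 and 11.4.2 slot unscheduled readings into these windows, so the two documents are in tension and the protocol sentence does not settle the matter.

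Several limiting points stand:

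- Readings on Days 12–14 should be rare. The Day 10 and Day 15 PK windows are single days, so a visit moved to one of these days would miss its PK window as well.
- By-visit displays show only visits where the parameter is planned. Double use is therefore visible only if vital signs are planned at both Day 10 and Day 15. Table 9 has rows for both, but that is not proof, because SAP 11.2 applies windows even where a parameter is not scheduled. The injection-phase schedule grid was not legible enough to confirm it.
- Windows of 10–11 and 12–16 would also remove the overlap. Starting at 13 is an inference from the midpoint pattern, which has an exception: the midpoint of Days 2 and 5 is 3.5, yet Day 3 goes to Day 5.

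A reader might also infer that the selection rule favours unscheduled over scheduled readings, or that the Day 15 summary is pulled toward abnormal values. The documents support neither. The rule ranks by distance and ignores scheduled status; against a Day 15 reading only Day 14 wins. Nothing in the documents says how often unscheduled vital signs follow an abnormal value. Protocol Section 8 mentions unscheduled samples for safety or technical reasons, without a frequency.

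**Conclusion.** The point holds as a minor error in an operative rule. Table 9 allows a Day 12 vital-sign reading to serve two visits. Its target of 14 lets a Day 14 reading replace the Day 15 reading and a Day 13 reading be averaged with it. The overlap causes the double use; the target causes the displacement. The closest-to-target rule does not create the double use, but it does not prevent it either.

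The impact is confined to descriptive vital-sign summaries for the few participants, if any, with off-schedule readings on Days 12–14. No claim of bias in either direction is made. Day 15 PK slotting is unaffected, because its window is the single Day 15 whatever target is printed. The conclusion assumes that programmers apply Table 9 and SAP 11.5.1 as written, without an unstated first-match rule, and that vital signs are planned at the visits concerned.

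**What to change.** In SAP Table 9, change the lower bound of the Day 15 vital-sign window from 12 to 13 and its target day from 14 to 15. For consistency, set the Day 15 PK target to 15 as well; this alters no result. It would also help to add one sentence saying how the slotting of unscheduled readings fits with Protocol 10.4.1, since the two edits alone do not reconcile those texts.

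The cost is two numbers, a third that is cosmetic, and an optional sentence. No data collection changes. SAP 1.1 labels the document as critical components and SAP 11.9 foresees a full version, so the correction can be made there before the vital-sign tables are programmed.

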OLI phase: 
 
If Assessment Date < First Dose Date of Oral CAB + RPV then 
 
Phase Day = Assessment Date – First Dose Date of Oral CAB + RPV
 
 
 
If Assessment Date <math>\geq</math> First Dose Date of Oral CAB + RPV then 
 
Phase Day = Assessment Date – First Dose Date of Oral CAB + RPV +1
 
 
 

Injection phase: 
 
If Assessment Date < Dose Date of Injection CAB + RPV then 
 
Phase Day = Assessment Date – Dose Date of Injection CAB + RPV
 
 
 
If Assessment Date <math>\geq</math> Dose Date of Injection CAB + RPV then 
 
Phase Day = Assessment Date – Dose Date of Injection CAB + RPV +1
 
 
 

Follow-up phase: 
 
If Assessment Date < Follow-up Week 4 Visit Date then 
 
Phase Day = Assessment Date – Follow-up Week 4 Visit Date
 
 
 
If Assessment Date <math>\geq</math> Follow-up Week 4 Visit Date then 
 
Phase Day = Assessment Date – Follow-up Week 4 Visit Date +1
 
 
 

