### 11.9.6. Pharmacokinetic Tables

Pharmacokinetic: Tables					
No.	Population	GSK Standard / Example Shell	Title	Programming Notes	Deliverable [Priority]
Pharmacokinetic Parameters					
4.1.	PK Parameter	PK_01	Summary of Derived Plasma Cabotegravir PK Parameters by Study Phase		Interim, SAC
4.2.	PK Parameter	PK_01	Summary of Derived Plasma Rilpivirine PK Parameters by Study Phase		Interim, SAC
Pharmacokinetic Concentration					
4.3.	PK Concentration	PK01	Summary of Plasma Cabotegravir PK Concentration (ug/mL)-Time Data by Study Phase and Nominal Timepoint		SAC
4.4.	PK Concentration	PK01	Summary of Plasma Rilpivirine PK Concentration (ng/mL)-Time Data by Study Phase and Nominal Timepoint		SAC

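### SAP Table 9 sets follow-up windows in days since injection but tests them against a day count that starts at the Week 4 visit, so Week 12 labs and vital signs fall in no window

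*SAP*

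**What the plan says.** SAP 11.2 (Appendix 2) assigns all assessments to analysis visits "according to actual dates of collection rather than the nominal visit labels recorded on the eCRF". By-visit displays then report only the visits at which a parameter is planned.

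In the follow-up block of Table 9 the target days are 56, 84, 168, 252 and 364 for Weeks 8, 12, 24, 36 and 52. The Week 8 row for labs and vital signs runs up to Injection Phase Day 70. The other nine rows use Follow-up Period Day:

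- Week 12 labs and vital signs: "71 ≤ Follow-up Period Day ≤ 126". Weeks 24, 36 and 52 follow at 127–210, 211–308 and 309 onward; the last row also covers ECG.
- Week 8 PK: "53 ≤ Follow-up Period Day ≤ 59". The other PK rows are 81–87, 165–171, 249–255 and 361–367.

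Anything that matches no row is labelled Day X. The table note says "OLI Day, Injection Day, and Follow-up Day are defined in Section 11.5.1". There, the formula for dates on or after the Week 4 visit is "Phase Day = Assessment Date – Follow-up Week 4 Visit Date +1".

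For PK concentrations, SAP 8.1 says "Nominal times will be used for the purposes of summarization and in mean and median plots". The title of Table 4.3 agrees: "Summary of Plasma Cabotegravir PK Concentration (ug/mL)-Time Data by Study Phase and Nominal Timepoint". Table 4.4 is the rilpivirine counterpart.

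**The concern.** The windows and the variable tested against them have different starting points. The targets are whole weeks since injection, matching protocol 4.1.4, which plans the follow-up visits at Weeks 8, 12, 24, 36 and 52 after the injections. The variable starts at Day 1 on the Week 4 visit.

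Two outputs are at stake. First, Tables 3.25, 3.26, 3.28, 3.29 and 3.37 (chemistry and hematology values and changes, and vital-sign changes, by visit) would contain no on-schedule Week 12 data. Second, the PK concentration summaries would depend on which of two rules the programmer follows, and under one of them Week 12 levels could be reported as Week 8.

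**Working it through.** **Inputs.** Injection Phase Day counts the injection date as Day 1, and Follow-up Day counts the Week 4 visit as Day 1 (both SAP 11.5.1). The Week 4 visit is on Injection Phase Day 28 (SAP Table 9). The windows are those listed above. A visit tolerance of ±3 days is used. It appears in the SAP schedule of activities and matches the width of the PK windows (56 ± 3 = 53–59); applying it to labs and vital signs is an assumption.

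**The plan's own targets.** 7 × 8 = 56, 7 × 12 = 84, 7 × 24 = 168, 7 × 36 = 252, 7 × 52 = 364. All five are weeks since injection.

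**Conversion.** Follow-up Day = Injection Day − 28 + 1 = Injection Day − 27.

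| Visit | Injection Day | Follow-up Day | Labs/vitals window met | PK window met (if Table 9 governs) |
|---|---|---|---|---|
| Week 8 | 56 | 29 | Week 8 (via Injection Day ≤ 70) | none |
| Week 12 | 84 | 57 | **none** (84 > 70; 57 < 71) | **Week 8** (53–59) |
| Week 24 | 168 | 141 | Week 24 | none |
| Week 36 | 252 | 225 | Week 36 | none |
| Week 52 | 364 | 337 | Week 52 | none |

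**Labs and vital signs.** A record is lost when Injection Day > 70 and Follow-up Day < 71, that is, when Injection Day < 71 + 27 = 98. The gap is Injection Days 71–97, or 27 days. At ±3 days, Week 12 is missed on 7 of 7 days and the other four visits are right on 28 of 28, so 28 of 35 visit-days are correct. The row labelled Week 12 would accept only Injection Days 98–153 (71 + 27 to 126 + 27).

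**PK, only if Table 9 governs.** Within ±3 days, Week 12 has Follow-up Days 54–60. Six of the seven fall in the Week 8 window and one (60) falls in none. The other four visits match no window on any day. Correct labels: 0 of 35. On the protocol's Table 2 medians (model predictions for gluteal injection), a Week 8 row filled with Week 12 values would show 0.58 instead of 0.91 for CAB (0.58/0.91 − 1 = −36%) and 13.5 instead of 20.3 for RPV (13.5/20.3 − 1 = −33%).

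**Sensitivity.** In general the gap runs from Injection Day 71 to 69 + the Week 4 day. With Week 4 on Days 25 to 31 (an assumed range) it runs from 71–94 (24 days) to 71–100 (30 days), and the counts of 28/35 and 0/35 do not change. On a wider grid (Week 4 on Days 25–32, later visits from 3 days before to 4 days after target, 64 combinations per visit), Week 12 labs and vital signs meet no window in 64 of 64. No PK visit is ever correctly labelled; Week 12 PK is labelled Week 8 in 43 of 64 and gets no label in 21.

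**With Injection Phase Day on every row.** All five visits fall in their own windows: 35 of 35 for labs and vital signs, 35 of 35 for PK.

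**The case against.** - *The Phase Day entry in 11.5.1 opens by counting from the first CAB + RPV dose of the respective phase.* No dose is given in follow-up, so one could take the injection as the anchor, and then every row of Table 9 works. But the explicit follow-up formula names the Week 4 visit, and a specific formula overrides a general lead-in. What stands is that 11.5.1 is inconsistent with itself and should be tidied too.
- *The loss matters only if labs and vital signs are planned at Week 12.* The schedule grid is broken in the copy available for review, so this cannot be read from it directly. Table 9, however, lists these parameters at selected visits only and has a Week 12 row for both, and protocol 4.1.4 plans safety assessments at Week 12. That is good evidence, though not confirmation.
- *PK summaries have their own rule.* SAP 8.1 and the table titles specify nominal time, and SAP 11.4.2 generally favours planned time. This is a reasonable reading, and it is why the PK part is conditional. But 11.2 covers all assessments, Table 9 carries PK rows, and no clause says which rule prevails.
- *The study is small and descriptive, the intent is clear, and an empty Week 12 row would be noticed.* This limits the consequence. It does not make the written rule right, and a plan should not rely on an undocumented correction by the programmer.

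**Conclusion.** The point holds. As written, on-schedule Week 12 labs and vital signs match no window and drop out of five by-visit tables. This is true for every Week 4 and Week 12 timing tried, assuming that those parameters are planned at Week 12. Weeks 8, 24, 36 and 52 enter the correct windows for labs and vital signs. One qualification is that 11.5.1 picks the record closest to target when a window holds several. At Week 24 the planned visit (Follow-up Day 141) lies 27 days from target 168, so an unscheduled repeat on Injection Day 182 (Follow-up Day 155, 13 days away) would displace it.

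The PK mislabelling is real only if Table 9 governs the concentration summaries, which the SAP leaves open. The percentages above illustrate that reading and are not thigh data.

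The primary PK parameters are safe, because "All calculations of non-compartmental PK parameters will be based on actual sampling times". Adverse-event and worst-grade summaries and listings are also unaffected. The error is therefore confined to by-visit descriptive output, but it is an error in a stated rule and should be corrected before the tables are programmed.

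**What to change.** In the follow-up block of SAP Table 9, replace Follow-up Period Day with Injection Phase Day on all nine rows that use it, keeping the limits as they are: PK 53–59, 81–87, 165–171, 249–255 and 361–367; labs and vital signs 71–126, 127–210 and 211–308; labs, vital signs and ECG from 309. Use Injection Phase Day in the follow-up Day X row as well, so that unslotted records carry the same day count.

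Add one sentence to 8.1 or 11.2 saying whether nominal time or the Table 9 windows govern PK concentration summaries and plots. While editing, reconcile the opening sentence of Phase Day in 11.5.1 with its follow-up formula. The Table 9 change works whichever way that is settled.

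The cost is SAP wording only, with no new data.
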